#### 4.4.2. Handling of Participant Withdrawals or Termination

If a subject is removed or withdraws from the study, the date and reason for withdrawal will be recorded on the appropriate electronic case report form (eCRF). If the subject is withdrawn due to an adverse event (AE) or serious adverse event (SAE), the Investigator will follow the subject until the AE/SAE has resolved or is considered stable. The local CHU will collect the resolution information of any reported SAEs.

If a subject is unable to return for an office/clinic visit or cannot be contacted by telephone, 3 separate telephone calls should be made to obtain subject related safety information. All attempts should be documented in the source documents. If the subject does not respond to the 3 telephone calls, then the investigator must send a certified letter to the subject. If the subject does not respond to the letter, then the subject will be considered "lost to follow-up" for the study.

Subjects who have signed the ICF but are later found not to be eligible PRIOR to insertion of the study catheter will be excluded and might not count for the enrollment goal. Excluded subjects can be replaced with new enrolled subjects for the study to reach a total of the predefined evaluable study-subjects (up to 50).

## 4.5. Subject Enrollment Disposition

The following subject groups are defined:

- Enrolled Subjects: Patients who sign the informed consent form.
- Excluded Subjects: Subjects who are enrolled but never undergo insertion of the study catheter.
- **Discontinued Subjects**: Enrolled subjects who have the study catheter inserted but do not undergo ablation (no RF energy is delivered with the study catheter and the nGEN generator).

- Lost to Follow-up Subjects: Subjects for whom contact is lost after most recent visit (despite 3 documented attempts to contact the subject).
- Withdrawn / Early Termination Subjects: Subjects who withdraw consent for study participation or are withdrawn by the investigator, are terminated from the study prior to completion of all follow-up visits.
- **Completed Subjects:** Enrolled subjects who have not been excluded, discontinued, expired, withdrawn, terminated early, or lost-to-follow-up from the study prior to the final study visit.

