#### 8.2.2.3 Recommended AF Ablation Procedure Sequence

Subjects will arrive to the electrophysiology laboratory for their ablation procedure and will undergo preparation for the procedure per the hospital's standard protocol (discretion of investigator).

*The AF ablation procedure workflow is recommended to follow the sequence below:* 

- Anesthesia or sedation should be delivered per standard EP lab procedure.
- Placement of diagnostic catheters
- Cardioversion if subject not in sinus rhythm (per investigator discretion)
- CARTO® Respiratory Gating (unless using Jet Ventilation)
- Administration of heparin bolus prior to transseptal puncture or immediately following transseptal puncture
- Transseptal puncture
- Following successful transseptal puncture, an anatomic map can be performed, utilizing Lasso® or PentaRay® (or other at investigator discretion)
  - Note: An anatomical map is not required for triggers outside the left atrium (e.g. SVC/CS etc.)
- Placement of esophageal temperature monitoring device (per investigator discretion)

- Confirmation of target ACT is ≥325 sec (but preferable 350 sec) prior or immediately after transseptal but no later than first ablation into the left atrium and maintain throughout the procedure
- Introduction of the QDOT MICRO™ catheter
  - Use the AUTOTAG feature in CARTO® 3 (Version 6.0 or above) to tag each QMODE+ ablation point after each application
  - At the new location ensure catheter stability before commencing RF application.
  - A pre-ablation flow rate delay of minimal 2 seconds will occur before RF application
  - Ablation modality: RF power application of up to 90W for up to 4 seconds (QMODE+)
  - Move the catheter to a new location (~4mm) if clinically effective ablation is achieved
  - QMODE+ should be used for full PV encirclement. If the investigator deems that QMODE+ is unable to achieve PVI, the study catheter in QMODE should be used to complete the procedure
  - $\circ$   $\,$  Continue RF applications and catheter movement until the circumferential PVI is completed.
  - Precautions:
    - If the temperature increases above the temperature cutoff (default 65°C), RF application will stop immediately (automatically)

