### 8.2.3. Data Collection During Study Ablation Procedure

Procedural data collection will be done through generator files, CARTO® datafiles, procedural worksheets and subject medical files. Documentation of procedural data will be kept in the subject's CRF, back-up generator files and back-up CARTO® log files for study analysis.

At the completion of the study ablation procedure two back-up copies of the CARTO® 3 and generator log files will be made. One copy should be kept at the site within the investigator site or patient binders, and one fully anonymized copy will be sent to the sponsor, in a timely manner

The Carto and Generator data (electronic raw data) collected during the Study Ablation procedure will be anonymized (or de-identified) prior to its transfer to the Sponsor. Data will be verified during this lifecycle (Data Transfer) to ensure the records are complete and are traceable to subjects within each clinical site. Data will be archived per the applicable policies and procedures as it relates to Data Extract process, Record Retention etc., and will be the source for data analysis. During data transfer, redundant copies will be stored at each critical stage of the transfer to safeguard adequate control over business continuity or disaster recovery of records. A copy of the electronic raw data will also be stored at each clinical site until receipt and storage by the sponsor has been confirmed.

The information collected during the procedure will include, but will not be limited to, the list below.

- RF application-mode per lesion (QMODE+ /QMODE)
- Number of RF applications with QDOT MICRO™ catheter (total/QMODE+/QMODE)
- Duration of RF applications with QDOT MICRO™ catheter (total/QMODE+/QMODE)
- PVI ablation time (time between first RF application and last RF application on a PV before isolation confirmed and circumferential ablation achieved)
- Subject PVI ablation time (time between first RF application and last RF application before all PVI complete)
- Subject total ablation time (time between first RF application and last RF application in a subject)
- Ablation parameters per RF application from the generator files
- Touch-up applications
- Total procedure time (from first femoral puncture to last catheter removal)
- Mapping time
- Fluoroscopy time
- LA catheter dwell time (from ablation catheter LA insertion to ablation catheter removal from the LA)
- ECG data

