## 14.2. Analysis Sets

The following analysis populations will be used to complete the analyses of data:

- **Safety Analysis Set**: The Safety Analysis Set will include all enrolled subjects who have the investigational device inserted, regardless if RF energy is delivered.
- Effectiveness Analysis Set : The effectiveness analysis set will include all enrolled subjects who meet the study eligibility criteria, have the investigational device inserted and undergo an ablation procedure with the study catheter used in conjunction with QMODE+ and /or QMODE for PVI (RF energy is delivered). The subjects without any QMODE+ applications for PVI will be considered a failure.

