### 14.4.6. Analyses of Secondary Safety Endpoints

Secondary safety endpoints will be analyzed using the safety analysis population.

An adverse event (AE) is an event recorded on the Adverse Event CRF page with an onset on or after the study ablation procedure. AEs with onset prior to this date that worsen in severity (i.e., increases in severity) after a subject has signed informed consent OR have a missing onset date are also considered an AE. AEs will be summarized both by subject and event. If a subject has multiple occurrences of an AE, for the by-subject summary only a single occurrence will be counted and for the by-event summary each event will be counted.

The overall incidence of AEs will be summarized by:

- Any adverse event;
- Serious adverse event;
- Non-serious adverse event;
- Device-related adverse event (defined as unlikely, possible, probable or having a causal relationship with the device);
- Serious device-related adverse event;
- Unanticipated device-related adverse event;
- Serious unanticipated device-related adverse event;
- Procedure-related adverse event (defined as unlikely, possible, probable or having a causal relationship with the procedure);
- Adverse events leading to discontinuation.

Serious AEs (SAE) and Non-Serious AEs (NSAE) will be summarized separately by overall incidence and adverse event term using categorical summaries.

An adverse device effect (ADE) is any event recorded to have led to an AE on the Investigational device deficiency CRF.

ADEs will be summarized by overall incidence, ADEs leading to an AE, ADEs leading to an SADE and unanticipated SADE (USADE), device, and time point during the procedure using categorical summaries.

Serious Adverse ADEs (SADE) will be summarized by overall incidence, SADEs leading to an AE, SADEs leading to a USADE, device, and time point during the procedure using categorical summaries.

ADEs, SADEs, and USADEs will be summarized by overall incidence and by adverse event term using categorical summaries in separate tables.

Listings of adverse events and device effects will be generated as well as device deficiencies.

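### The procedure-related AE incidence covers only subjects who had the study catheter inserted, so a complication that ends the case earlier in the procedure enters no summary rate

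*Combined protocol and SAP*

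**What the plan says.** **Safety set.** Under 14.2 the Safety Analysis Set "will include all enrolled subjects who have the investigational device inserted, regardless if RF energy is delivered". Section 4.5 defines Excluded Subjects as "Subjects who are enrolled but never undergo insertion of the study catheter", with no condition on why insertion did not happen.

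**Use of the set.** Section 14.4.6 opens with "Secondary safety endpoints will be analyzed using the safety analysis population". The incidence categories that follow include procedure-related AEs, listed separately from device-related AEs. Under 14.4.1, AE percentages take the analysis population as their denominator.

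**Order of steps.** The recommended sequence in 8.2.2.3 lists diagnostic catheters, heparin and transseptal puncture first. It continues: "Following successful transseptal puncture, an anatomic map can be performed". The QDOT MICRO catheter is introduced only after that. The Protocol Summary likewise lists left atrial mapping before the study catheter. Section 8.2.3 starts the procedure clock at first femoral puncture.

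**Replacement.** Section 4.4.2 states that "Excluded subjects can be replaced with new enrolled subjects". The sentence before it concerns subjects "later found not to be eligible PRIOR to insertion of the study catheter will be excluded and might not count for the enrollment goal".

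**The concern.** An insertion-based set is a normal choice for device-related events, because it contains the subjects exposed to the device. It fits a procedure-related rate less well. By the protocol's own timing the procedure has begun at femoral access, and Section 9.2.2 grades relationship to the procedure on its own scale, separately from relationship to the device. The planned rate leaves out the early part of the procedure in exactly those cases where that part goes badly enough to stop.

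Section 1.2.1 names acute safety as a main objective, and Section 14.3 relies on 30 to 50 subjects to characterize it. With so few subjects, one serious access or transseptal complication decides whether a reported incidence is zero.

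**Working it through.** There is no planned figure to reproduce: the study is descriptive, with no power calculation (14.1, 14.3). The check traces one subject through the rules and then does simple arithmetic.

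**Step 1: follow one subject.** Suppose a tamponade occurs at transseptal puncture and the case is stopped before the study catheter goes in.

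| Rule | Result |
|---|---|
| 9.4.1: AEs recorded from consent | Event collected |
| 9.4.1, Table 9: SAEs to sponsor within 72 hours | Event reported |
| 9.4.2: sponsor complaint review, Health Canada, ethics board | Event reviewed and reported as required |
| 14.4.6: AE onset on or after the study ablation procedure | Meets the SAP definition, if the procedure starts at femoral puncture |
| 4.5: no insertion | Subject is Excluded |
| 14.2: insertion required | Not in the safety set |
| 14.4.1 and 14.4.6: rates on the safety set | In neither numerator nor denominator |
| 14.4.2: disposition | Counted as excluded |

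The population rule alone removes the event from the rates. No section provides an AE summary for enrolled subjects outside the safety set.

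**Step 2: effect of one such case.** Take *n* inserted subjects, *x* of them with an event, plus one subject whose case stopped before insertion. The planned rate is *x/n*. The full rate is *(x + 1)/(n + 1)* if the stopped subject had an event and *x/(n + 1)* if not.

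| Scenario | Planned | With the stopped subject |
|---|---|---|
| n = 30, x = 0, stopped with event | 0/30 = 0.0% | 1/31 = 3.2% |
| n = 50, x = 0, stopped with event | 0/50 = 0.0% | 1/51 = 2.0% |
| n = 30, x = 1, stopped with event | 1/30 = 3.3% | 2/31 = 6.5% |
| n = 50, x = 1, stopped with event | 1/50 = 2.0% | 2/51 = 3.9% |
| n = 30, x = 1, stopped without event | 1/30 = 3.3% | 1/31 = 3.2% |

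The SAP plans no intervals. For scale, exact (Clopper-Pearson) 95% intervals are 0 to 11.6% for 0/30 and 0.08 to 16.7% for 1/31; they are 0 to 7.1% for 0/50 and 0.05 to 10.5% for 1/51. The shift is well inside the imprecision of the study.

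**Step 3: how often.** The documents give no rate for events before insertion that stop the case. Section 1.3.1 gives whole-procedure rates from any cause, which can serve only as ceilings. Expected events = rate × n.

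| Rate in 1.3.1 | n = 30 | n = 50 |
|---|---|---|
| Tamponade 0.2% to 5% | 0.06 to 1.5 | 0.1 to 2.5 |
| Tamponade 0.18% (2,750 procedures) | 0.054 | 0.09 |
| Tamponade 0.8% (34,943 procedures) | 0.24 | 0.4 |
| Vascular injury 0.2% to 1.5% | 0.06 to 0.45 | 0.1 to 0.75 |

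At the two rates with a stated number of procedures, fewer than half a tamponade is expected at any stage. The share before insertion is smaller by an unknown amount, and many vascular injuries need not stop a case.

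**The case against.** The strongest reply is that this is a descriptive workflow study of one catheter-generator system. An insertion-based set isolates exposure to that system, and an access complication before insertion says nothing about it. That stands for the device-related rates, and it is why the safety set should stay. It does not answer for a rate labelled procedure-related.

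Four stronger readings may tempt a reader, and the documents do not support them.

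- **That such events go unreported.** They do not. They are collected from consent, expedited if serious, reviewed by the sponsor and open to aggregate safety review (9.4.1, 9.4.2, 9.5). Section 14.4.6 also promises AE listings, and it is unclear whether its opening population sentence governs them. The gap is in the summary incidence.
- **That the subject will be replaced.** Section 4.4.2 allows replacement of excluded subjects straight after a sentence about ineligibility, so it may cover only ineligible subjects. The definition in 4.5 is wider and would permit replacement. The text does not settle this, and the omission does not depend on it.
- **That the planned rate is always too favourable.** A case can also stop before insertion without an AE. For example, 8.2.1 allows imaging for thrombus on the procedure day, and thrombus is an exclusion. Such subjects would enlarge the denominator and lower the rate, as the last scenario in Step 2 shows.
- **That the published complication rates measure the loss.** They cover the whole procedure. Section 1.3.1 gives no rate for transseptal puncture.

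It is also fair that the sequence in 8.2.2.3 is only recommended, and that insertion is not defined as entry into the left atrium. A subject whose study catheter is already in the body may count as inserted. That narrows the gap without closing it.

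**Conclusion.** The point holds in limited form. Followed exactly, the plan gives a procedure-related AE incidence that leaves out complications ending the case before study-catheter insertion, and no other summary picks them up. One such case is worth about 3.2 percentage points at 30 inserted subjects and 2.0 at 50 when no other event occurs. Its frequency is not given and is probably low. No test, threshold or decision rule changes, so this is a completeness improvement and not a flaw that undermines the study.

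The conclusion rests on two assumptions. First, the steps are carried out in the recommended order. Second, the inserted device in 14.2 means the study catheter. Section 6.7 lists only the generator as investigational, and a generator is not inserted, so 4.5 supplies the sensible meaning.

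**What to change.** Keep the safety set as defined for device-related events. In 14.4.6:

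1. Add a count and a listing of AEs in enrolled subjects whose procedure had started (first femoral puncture) but who had no study catheter inserted.
2. State the procedure-related and the serious AE incidence a second time. The denominator is the safety set plus all such subjects, with or without an AE. The numerator adds those who had an AE.
3. State which population the AE listings cover.

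Two wording changes would help: name the study catheter in 14.2, and say in 4.4.2 whether replacement extends beyond ineligible subjects.

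The AE data are already collected, so the cost is one extra listing and one extra table row. The second figure may be slightly less favourable than the first. If no such case occurs, the row reads zero and shows that nothing was left out.

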# 5. Responsibilities

# 5.1. Investigator Responsibilities

Investigators at each participating clinical site will have the following responsibilities:

- Assuring compliance by site personnel with the provisions of the protocol
- Providing the Sponsor with:
  - Signed, dated Investigator Agreement
  - Written EC approval letters and EC-approved consent forms
  - o Signed, dated Financial Disclosure form for each participating investigator
  - o Curriculum vitae for each investigator
- Maintain an accurate and current Delegation of Authority log which identifies individuals authorized to perform work for the study and assuring compliance by site personnel with the provisions of the protocol
- Completing the appropriate training on the device (ablating investigators only) and the study protocol prior to enrolling and treating subjects
- Maintain accurate and current logs for the study such as:
  - Subject log, Device Accountability Log
- Obtain initial and amendment (if applicable) HC approval and annual review/approval thereafter for the study protocol and informed consent as applicable
- Obtain informed consent form and enroll patients
- Perform medical procedures
- Order tests required by the study protocol
- Review pre-procedure imaging pertaining to the pulmonary vein size prior to treatment
- Follow subjects until the end of the study protocol
- Accurately complete and sign eCRFs in a timely manner
- Maintain relevant source documentation and allow Sponsor direct access to perform monitoring or auditing duties
- Maintain records and provide reports according to prevailing regulatory requirements
- Share relevant study-related information with delegated study staff
- Inform the appropriate entities (e.g., Sponsor, HC) in a timely manner regarding the occurrence of AEs and/or product malfunctions.
- Making sufficient effort to maintain contact with treated subjects who fail to comply

with the follow-up requirements

- Maintain study records for at least 5 years or as specified per country specific record retention requirements after the study is completed and or terminated. The Sponsor will notify the Investigator of either of these events.
- Complying with HC and Sponsor annual report requirements, including the final report.

# 5.2. Sponsor Responsibilities

The Sponsor (Biosense Webster, Inc.) will be responsible for the following:

- Conduct of pre-study site assessment and approval.
- Preparation and modification (if applicable) of study documents including but not limited to the protocol, CRFs and informed consent
- Selection of appropriately qualified and trained individuals, including monitors, to conduct the study
- Conduct protocol and device training for investigators and research personnel as applicable
- Set-up of study-specific committees
- Obtain signed study contracts from investigators/hospitals, CROs and other involved parties
- Ship study devices to each site
- Monitor sites for the duration of the study
- Maintain study database
- Inform investigator of his/her responsibilities
- Submit and obtain approval for study from applicable regulatory agencies
- Preparation of reports summarizing the status of the study no less than annually. These reports will be supplied to the Principal Investigator at each site.
- Update Report of Priors, IFU, IB, and Risk Analyses, as applicable
- Update investigators on safety issues, if needed
- Report to study investigators and regulatory agencies, as required
- Have AEs reviewed by the study-specific committees, as required
- Communications with the competent authority
- Submission of any amendments to the Clinical Study Protocol/Post market clinical follow up plan to the competent authority.

## 6. Study Device Description

#### 6.1. Device Acquisition

After obtaining a fully executed clinical trial agreement and appropriate HC approvals, the sponsor will initiate shipment(s) of the investigational device to the site. The Sponsor will keep records of all investigational devices shipped to the site. Approved investigational devices will be shipped directly to the site and will be received by the site. Investigators are responsible for appropriate logging of

the devices received, verification of packing slip information (i.e., lot numbers and quantity shipped), date and identity that each device was used in the study, disposition information regarding disposal or return to the Sponsor.

# 6.2. Device Storage and Stability

Devices are to be stored in accordance with the IFUs and User Manual. Do not use this device after the "Use By" date.

## 6.3. Device Preparation

Information related to device preparation can be found in the IFUs.

## 6.4. Instructions for Use

A comprehensive set of IFU/User manuals for the QDOT MICRO™ System, and all accessory cables/interface cables is contained in each product package and is also available upon request.

#### 6.5. Device Description

[figure not shown]
#### 6.5.1. QDOT MICRO™ Catheter

The Biosense Webster QDOT MICRO™ Navigation Catheter (Uni-Directional and Bi-Directional) and related accessory devices are indicated for catheter-based cardiac electrophysiological mapping (stimulating and recording) and, when used in conjunction with a compatible radiofrequency generator (including the nGEN Generator, D-1384-01), for cardiac ablation. The Biosense Webster QDOT MICRO™ Uni-Directional and Bi-Directional Navigation Catheter provides a real-time measurement of temperature and contact force between the catheter tip and heart wall, as well as location information when used with the CARTO™ 3 System.

The catheter has a high-torque shaft with deflectable tip section containing an array of electrodes which includes a 3.5 mm tip dome with three microelectrodes. All of the electrodes may be used for recording and stimulation purposes. The tip electrode serves to deliver RF energy from the RF generator to the desired ablation site. The tip electrode and ring electrodes are made from noble metals.

The catheter incorporates six thermocouple temperature sensors that are embedded in the 3.5 mm tip electrode.

At the proximal end of the catheter, a saline input port with a standard Luer fitting terminates from the open lumen. This saline port serves to permit the injection of normal saline to irrigate the tip electrode. During ablation, heparinized normal saline is passed through the internal lumen of the catheter and through the tip electrode, to irrigate and cool the ablation site as well as the electrode tip. An irrigation pump should be used to control the saline irrigation.

[figure not shown]

